16.6 Ophthalmoscopy

Dilated fundus exams will be performed at Visit 1 using indirect ophthalmoscopy. At Visit 5, undilated fundus exams will be performed unless dilation is necessary. The investigator will make observations of the vitreous, retina, macula, choroid and optic nerve.

Observations will be graded as Normal or Abnormal. Abnormal findings that are clinically significant (as determined by the investigator that may interfere with study parameters or otherwise confound the data)

and those that are not clinically significant will be described. An indirect Fundoscopy examination should be performed if retinal disease is detected.

The results will be summarized using counts and percentages for each treatment group at each visit for each eye (study eye and fellow eye). Percentages will be based on the number of subjects in each treatment group with responses. Shift tables for the fundoscopy parameters will also be provided comparing Visit 5 to baseline (Visit 1). A subject listing of the fundoscopy parameters will also be produced.

16.7 Conjunctival Redness Score

The Ora Calibra® Conjunctival Redness Scale for Dry Eye will be performed on all scheduled visits. Both pre- and post-CAE® assessments will be made at Visits 1 and 5. The conjunctival redness scale ranges from 0 to 4 where 0 = normal, without vasodilation, 1 = trace ciliary or conjunctival vasodilation, 2 = broad ciliary vasodilation, 3 = broad ciliary and slight, horizontal conjunctival vasodilation, and 4 = broad ciliary and prominent, horizontal conjunctival vasodilation. Half unit increments are allowed.

Conjunctival redness will be summarized by treatment group, visit and time point (pre- and post-CAE®) using quantitative summary statistics. Change from baseline will be also summarized.

16.8 Vital Signs

Each subject will have vital signs assessments (resting blood pressure and pulse) conducted at Visits 1, 2, and 5. Vital signs are to be conducted by a qualified staff member who may be any of the following: a board-certified investigator or sub-investigator, nurse practitioner, registered nurse, or physician assistant.

Systolic and diastolic blood pressure should be measured in the same arm each time using a sphygmomanometer with the subjects who have been in a resting state (seated upright) at least 5 minutes. Blood pressure will be recorded in mmHg.

Pulse will be measured with the subjects who have been in a resting state (seated) for at least 5 minutes. Pulse will be counted for 30 seconds and multiplied by 2, and recorded in beats per minute (bpm).

The vital signs and changes from baseline will be summarized using continuous descriptive statistics by visit for each treatment group and for all actively treated subjects. A subject listing of vital signs will also be produced.

Vital signs will also be presented categorically for the number of subjects with low, normal, or high values as defined by the table below:

Vital Signs	Low	Normal	High
Systolic Blood Pressure (mmHg)	<90	90-180	>180

Vital Signs	Low	Normal	High
Diastolic Blood Pressure (mmHg)	<50	50-100	>100
Pulse Rate (bpm)	<50	50-110	>110

16.9 Laboratory Tests

Samples of blood (non-fasting) and urine will be collected at Visits 1 and 5 and evaluated for blood chemistry, hematology, and urinalysis. Parameters will be summarized using continuous descriptive statistics by visit for each treatment group and for all actively treated subjects. A subject listing will also be produced.

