8.2 Safety Measures

For stages 1 and 2, the following safety measures will be examined:

- Adverse events (ocular and non-ocular)
- Ora Calibra® Drop Comfort Assessment
- Best-corrected visual acuity (BCVA)
- Slit-lamp biomicroscopy
- Intraocular pressure (IOP)
- Ophthalmoscopy
- Ora Calibra® Conjunctival Redness for Dry Eye Scale
- Vital signs
- Laboratory tests (chemistry, hematology, urinalysis)
- Urine pregnancy test

Laboratory test results will be forwarded from the central laboratory to the study site and to AxeroVision Inc. or its designee. The laboratory results from screening will be reviewed prior to randomization. Laboratory tests at screening may be repeated once at the discretion of the investigator and pending discussion with AxeroVision Inc., to confirm exclusionary status. Study treatment will be performed only if the investigator deems the laboratory results to be acceptable. The most current specimen results will be reviewed prior to randomization. The investigator will review all laboratory results for the clinical significance of any abnormalities. Evaluation and management of abnormal laboratory results should be conducted according to local site practice. Clinically significant abnormalities are to be recorded on an adverse event electronic case report form (eCRF) page.

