APPENDIX 3: HANDLING OF BIOLOGICAL SPECIMENS

Blood sample will be collected for hematology (3 mL per draw), serum chemistry (4 mL per draw), pharmacokinetics (6 mL per draw + 5mL for heparin/saline flush for post-dose draws, 6 mL per draw for the pre-dose V2 and V4 draw. The approximate collection amounts per visit are described below:

	Approximate Blood Collection Amounts per Visit			
	Visit 1	Visit 2	Visit 4	Visit 5
Hematology	3mL	N/A	N/A	3mL
Serum Chemistry	4mL	N/A	N/A	4mL
PK	N/A	6mL	71mL	N/A
Total	7mL	6mL	71mL	7mL

- Hematology includes leucocytes, erythrocytes, Hgb, Hematocrit (Hct), Mean Cell Volume (MCV), Mean Cell Hemoglobin (MCH), Mean Cell Hemoglobin Concentration (MCHC), thrombocytes, and partial automated differentiation: lymphocytes, neutrophils, monocytes, eosinophils, and basophils.
- Serum Chemistry includes sodium (Na), potassium (K), chloride (Cl), bicarbonate (CO₂), calcium (Ca), phosphorus (P), blood urea nitrogen (BUN), creatinine, albumin, globulin, glucose, cholesterol, low density lipoprotein (LDL), high density lipoprotein (HDL), triglycerides, alanine aminotransferase (ALT), aspartate aminotransferase (AST), lactate dehydrogenase (LDH), alkaline phosphatase (Alk Phos), gamma GT, and total bilirubin (any total bilirubin > ULN should be fractionated for direct bilirubin).
- Urinalysis includes appearance, glucose, ketones, Hgb, protein, nitrate, bilirubin, specific gravity, hydrogen ion concentration (pH), urobilinogen, and leucocytes. If positive for blood or protein trace, then microscopy will be included.
- Pharmacokinetics testing for AXR-159.

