8.4 Data Analysis Conventions

All data analysis will be performed by Statistics & Data Corporation (SDC) after the study is completed and the database has been locked and released for unmasking. Statistical programming and analyses will be performed using SAS® Version 9.4 or higher. Output will be provided in rich text format (RTF) for tables and portable document format (PDF) for tables, listings, and figures using landscape orientation. All study data will be listed by subject, treatment, and visit (as applicable) based on all randomized subjects unless otherwise specified.

Summaries for continuous and ordinal variables will include the number of observations (n), arithmetic mean, standard deviation (SD), median, minimum, and maximum). Minima and maxima will be reported with the same precision as the raw values; means and medians will be presented to one additional decimal place than reported in the raw values. SDs will be presented to two additional decimal places than reported in the raw values. Summaries for discrete variables will include frequency counts and percentages. All percentages will be rounded to one decimal place (i.e., XX.X%). Differences between active treatment groups and vehicle will be calculated as Active minus Vehicle and change from baseline will be calculated as follow-up visit minus baseline. The baseline measure will be defined as the last non-missing measure prior to initiation of investigational treatment.

Statistical comparisons between each AXR-159 Ophthalmic Solution group will be to the vehicle group at matched dosing frequency (TID or BID). AXR-159 Ophthalmic Solution plus Artificial Tear group will be compared to both AXR-159 Ophthalmic Solution and to the vehicle group at matched dosing frequency.

A final database lock will occur at the completion of Stage 2 and the safety, tolerability, and efficacy data from both Stage 1 and 2 will be analyzed separately and in a combined fashion to fully leverage the advantage of this two-stage study design.

All statistical tests will be two-sided with a significance level of 0.05 ($\alpha = 0.05$) unless otherwise specified. Confidence intervals (CI) for differences between treatment groups will be two-sided at 95% confidence. All p-values will be rounded to four decimal places; p-values less than 0.0001 will be presented as “<0.0001”; p-values greater than 0.9999 will be presented as “>0.9999”.

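### Laboratory tests get only continuous by-visit summaries and a listing, so newly out-of-range results that are not reported as adverse events are not counted by arm in any planned table

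*SAP*

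**What the plan says.** SAP 16.9 sets the sampling: "Samples of blood (non-fasting) and urine will be collected at Visits 1 and 5 and evaluated for blood chemistry, hematology, and urinalysis". Its only analysis rule, for all three panels, is: "Parameters will be summarized using continuous descriptive statistics by visit for each treatment group and for all actively treated subjects". It then adds: "A subject listing will also be produced".

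SAP 8.4 defines the statistics: "Summaries for continuous and ordinal variables will include the number of observations (n), arithmetic mean, standard deviation (SD), median, minimum, and maximum". It also has a general rule for other data: "Summaries for discrete variables will include frequency counts and percentages". SAP 8.3 says in general terms that changes from baseline are taken as visit minus baseline and summarised by treatment and visit.

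The SAP table list (section 20) has one laboratory table per stage and one combined (14.3.9.1 to 14.3.9.3). None is a shift or abnormality table.

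Protocol Appendix 3 gives the urine panel: "Urinalysis includes appearance, glucose, ketones, Hgb, protein, nitrate, bilirubin, specific gravity, hydrogen ion concentration (pH), urobilinogen, and leucocytes". Protocol 8.2 sets the route from laboratory result to adverse event: "Clinically significant abnormalities are to be recorded on an adverse event electronic case report form (eCRF) page".

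**The concern.** Safety and tolerability are primary objectives in both stages. The protocol synopsis states that this is the first time an antagonist of this class is given to humans as an eye drop. Scheduled laboratory safety consists of one sample before treatment and one at Month 3.

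Laboratory harm often appears as a few patients moving out of range rather than as a shift of the whole arm. By-visit distributions do not show how many patients crossed a limit, or whether an abnormal Visit 5 value was already abnormal at Visit 1. The two visit summaries also need not cover the same patients, since some with a Visit 1 sample may have none at Visit 5.

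The adverse-event route catches results that an investigator judges clinically significant, one patient at a time. Modest out-of-range changes that nobody reports individually, but that are more frequent on drug than on vehicle, would have no planned count by arm.

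**Working it through.** The documents state no figure for laboratory safety, so there is nothing to reproduce. The check is a comparison of sections, followed by an illustration.

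**1. Safety measures side by side**

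| Measure (SAP section) | Change from baseline stated | Category counts or shift table |
|---|---|---|
| BCVA (16.3) | yes | no |
| Slit-lamp (16.4) | not applicable (graded) | counts and shift table |
| IOP (16.5) | yes | no |
| Ophthalmoscopy (16.6) | not applicable (graded) | counts and shift table |
| Conjunctival redness (16.7) | yes | no |
| Vital signs (16.8) | yes | low/normal/high counts |
| Laboratory tests (16.9) | no | no |

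For vital signs the SAP adds: "Vital signs will also be presented categorically for the number of subjects with low, normal, or high values as defined by the table below". Every other numeric safety measure that is assessed at both baseline and follow-up and summarised by visit in sections 16.3 to 16.8 has its change from baseline written out. The table list agrees: slit-lamp and ophthalmoscopy have separate shift tables (14.3.5.2.x and 14.3.7.2.x), and laboratory tests have none. Protocol Table 4-1 lists shift tables for safety variables. Its examples are ocular and the list is open-ended.

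**2. Urinalysis**

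Appendix 3 names 11 items. Specific gravity and pH are plainly numeric, which leaves 11 − 2 = 9. That all nine would come back as grades is an assumption, because the documents do not give the laboratory's reporting format. Appearance cannot be averaged in any case. Section 16.9 makes no exception for such items.

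**3. Illustration for an enzyme in Stage 1 (assumed values)**

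Inputs: 48 active and 42 vehicle, the midpoints of the expected enrolment ranges 43–53 and 37–47 in SAP section 5. Assumed: SD 10 U/L, 4 active patients rising by 35 U/L (3.5 SD), none on vehicle.

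- Shift in active mean = 4 × 35 / 48 = 2.92 U/L.
- Active variance = 10² + (4/48)(44/48)(35²) = 100 + 93.6 = 193.6, so SD = 13.9.
- SE of arm difference = √(193.6/48 + 100/42) = √(4.03 + 2.38) = 2.53.
- z = 2.92 / 2.53 = 1.15; 95% half-width = 1.96 × 2.53 = 4.96 U/L.

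The 48 and 42 are enrolled numbers. With the plan's 10% dropout they become about 43 and 38. Then the shift is 140/43 = 3.26, the active variance is 100 + (4/43)(39/43)(1225) = 203.3, the SE is √(203.3/43 + 100/38) = 2.71, and z = 1.20. The conclusion does not change.

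**4. The same logic at the Stage 2 arm size**

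If k of n patients rise by r SD, the arm mean moves kr/n SD against a standard error of 1/√n SD. With n = 60 (SAP section 5), k = 2 and r = 3 (both assumed), the move is 6/60 = 0.10 SD against 0.129 SD, or 0.77 standard errors. For k = 1 to 3 and r = 2 to 5 the range is 0.26 to 1.94 standard errors. A shift table would show 2 of 60 (3.3%) directly.

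**5. What change from baseline would add**

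With equal variances at the two visits and correlation ρ, the SE of the mean change relative to that of a by-visit mean is √(2(1 − ρ)). This is 0.77 at ρ = 0.7 and 0.45 at ρ = 0.9 (ρ assumed). The paired summary would be tighter as well as restricted to the same patients.

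**The case against.** Several stronger readings are tempting, and the documents do not support them.

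- **That only means are planned.** SAP 8.4 includes SD, median, minimum and maximum. In the illustration the active SD rises from 10 to 13.9, and the maximum would probably rise too, so an attentive reader would get a hint. The hint is one extreme value per arm, with no count and no link to that patient's Visit 1 result.
- **That change from baseline is excluded.** SAP 8.3 has a general rule, and Protocol 12.4.1 says the same. Section 16.9 is unclear on this point; it does not contradict the rule.
- **That laboratory abnormalities cannot be seen by arm.** Clinically significant ones go to the adverse-event form, and SAP 16.1 tabulates non-ocular treatment-emergent events by treatment group. The gap is confined to results that are not reported that way.
- **That the Data Review Committee would miss a signal at the Stage 1 interim.** Protocol 6.1 has the committee evaluate all available safety data. Protocol 6.3 refers to a separate charter and analysis plan and allows ad hoc review, masked or unmasked. Neither of those documents is to hand. The listings would pair a patient's two visits, so counting by hand is possible.
- **That the SAP breaks a protocol commitment.** Protocol 12.4.7 does not ask for laboratory shift tables, and Table 4-1 does not name laboratory tests among its examples.

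Other points also count against the concern. SAP 8.4 already gives counts and percentages for discrete variables, which could be read to cover qualitative urinalysis. BCVA and IOP get no category counts either. Vital signs and Stage 1 pharmacokinetics add to the systemic picture, and the protocol expects negligible systemic levels. Finally, 4 of 48 against 0 of 42 gives a two-sided Fisher p of about 0.12, so the shift table would not settle the matter; it would only make the pattern visible.

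What remains is that no general rule in SAP 8.3 or 8.4 supplies out-of-range or shift counts for the numeric tests, and a listing is not an arm comparison.

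**Conclusion.** The point holds as a modest gap in safety reporting that is cheap to close. As written, SAP 16.9 and Tables 14.3.9.1 to 14.3.9.3 contain no low/normal/high or shift counts, leave change from baseline to be inferred from SAP 8.3, and apply continuous statistics to urinalysis items, several of which are not numeric. Newly out-of-range results are therefore counted by arm only when they are reported as adverse events.

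The size cannot be taken from the documents. On assumed values, a handful of patients with large individual rises moves the mean by roughly one standard error (1.15 in the Stage 1 example, 0.77 in the Stage 2 example). These figures show how the summary dilutes such cases and do not predict that such rises will occur. The comparison with other safety sections, and the absence of a laboratory shift table, rest on the text alone. The number of urinalysis items reported as categories depends on the laboratory's format.

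**What to change.** In SAP 16.9, with matching entries under Tables 14.3.9.x, add for each arm:

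1. Change from Visit 1 to Visit 5 for numeric chemistry, haematology and urinalysis parameters, using patients with both values.
2. A low/normal/high shift table from Visit 1 to the last post-baseline value, using the central-laboratory reference ranges. Taking the last post-baseline value also covers samples from early exits and unscheduled visits (Protocol 7.5 and 10.4.2), for which 16.9 has no rule.
3. Counts and percentages, with shift from Visit 1, for urinalysis items reported as categories, with a statement of which items those are.

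The laboratory results are already collected, so no extra samples are needed. The reference ranges are not in the documents and would have to come from the central laboratory; Appendix 3 already relies on an upper limit of normal for total bilirubin. The cost is programming and longer tables. Because blood is drawn non-fasting, some parameters may show out-of-range counts in both arms, so the counts should be read against vehicle.

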16.10 Urine Pregnancy Test

A urine pregnancy test will be conducted for females of childbearing potential at Visit 1 (Day -14 ± 2), Visit 5 (Day 85 ± 2), and may be conducted at an Unscheduled Visit. A listing of urine pregnancy test results will be generated.

17. Interim Analyses

An interim analysis will be performed when the last enrolled patient in Stage 1 completes Month 3 of the Expansion Cohort. There is no plan to stop the study for efficacy on the basis of the interim analysis. However, termination in individual dose groups due to safety, tolerability and/or futility may occur. Statistical significance will not be declared at the time of the interim analysis.

Given the exploratory nature of the study no Type I error adjustments will be made for the interim analysis including the Stage 1 data only.

18. Changes from Protocol-Stated Analyses

There are no changes from the protocol-stated analyses.

19. Revision History

The following revisions were made to SAP Version 2.0.

SAP Section	Revision	Rationale
12.1	Revised compliance calculation to use date of completion/discontinuation rather than date of last in-office instillation	Conservative estimation of compliance for discontinued subjects

12.2	Revised exposure calculation to use date of completion/discontinuation rather than date of last in-office instillation	Conservative estimation of exposure for discontinued subjects
13.1.1	Revised specification of random number seeds for MCMC	Consistency with 13.1.2
13.1.3, 13.1.4, 13.1.5	Revised specification of random number seeds for MCMC	Correction of seed specification

20. Tables

Tables that will be included in the topline delivery are shown in boldface font. Tables that will be included in the interim analysis are qualified as “Stage 1”.

Table Number	Title	Population
TABLE 14.1.1.1	SUBJECT DISPOSITION – STAGE 1	ALL RANDOMIZED SUBJECTS
TABLE 14.1.1.2	SUBJECT DISPOSITION – STAGE 2	ALL RANDOMIZED SUBJECTS
TABLE 14.1.1.3	SUBJECT DISPOSITION – COMBINED STAGE 1 AND STAGE 2	ALL RANDOMIZED SUBJECTS
TABLE 14.1.2.1.1	DEMOGRAPHICS – STAGE 1	MITT POPULATION
TABLE 14.1.2.1.2	DEMOGRAPHICS – STAGE 1	MITT2 POPULATION
TABLE 14.1.2.1.3	DEMOGRAPHICS – STAGE 1	SAFETY POPULATION
TABLE 14.1.2.2.1	DEMOGRAPHICS – STAGE 2	MITT POPULATION
TABLE 14.1.2.2.2	DEMOGRAPHICS – STAGE 2	MITT2 POPULATION
TABLE 14.1.2.2.3	DEMOGRAPHICS – STAGE 2	SAFETY POPULATION
TABLE 14.1.2.3.1	DEMOGRAPHICS – COMBINED STAGE 1 AND STAGE 2	MITT POPULATION
TABLE 14.1.2.3.2	DEMOGRAPHICS – COMBINED STAGE 1 AND STAGE 2	MITT2 POPULATION
TABLE 14.1.2.3.3	DEMOGRAPHICS – COMBINED STAGE 1 AND STAGE 2	SAFETY POPULATION
TABLE 14.1.3.1.1	OCULAR MEDICAL HISTORY – STAGE 1	MITT POPULATION
TABLE 14.1.3.1.2	OCULAR MEDICAL HISTORY – STAGE 2	MITT POPULATION
TABLE 14.1.3.1.3	OCULAR MEDICAL HISTORY – COMBINED STAGE 1 AND STAGE 2	MITT POPULATION
TABLE 14.1.3.2.1	NON-OCULAR MEDICAL HISTORY – STAGE 1	MITT POPULATION
TABLE 14.1.3.2.2	NON-OCULAR MEDICAL HISTORY – STAGE 2	MITT POPULATION
TABLE 14.1.3.2.3	NON-OCULAR MEDICAL HISTORY – COMBINED STAGE 1 AND STAGE 2	MITT POPULATION

Table Number	Title	Population
TABLE 14.1.4.1.1	CONCOMITANT OCULAR MEDICATIONS BY TREATMENT GROUP, DRUG CLASS AND PREFERRED NAME – STAGE 1	MITT POPULATION
TABLE 14.1.4.1.2	CONCOMITANT OCULAR MEDICATIONS BY TREATMENT GROUP, DRUG CLASS AND PREFERRED NAME – STAGE 2	MITT POPULATION
TABLE 14.1.4.1.3	CONCOMITANT OCULAR MEDICATIONS BY TREATMENT GROUP, DRUG CLASS AND PREFERRED NAME – COMBINED STAGE 1 AND STAGE 2	MITT POPULATION
TABLE 14.1.4.2.1	CONCOMITANT NON-OCULAR MEDICATIONS BY TREATMENT GROUP, DRUG CLASS AND PREFERRED NAME – STAGE 1	MITT POPULATION
TABLE 14.1.4.2.2	CONCOMITANT NON-OCULAR MEDICATIONS BY TREATMENT GROUP, DRUG CLASS AND PREFERRED NAME – STAGE 2	MITT POPULATION
TABLE 14.1.4.2.3	CONCOMITANT NON-OCULAR MEDICATIONS BY TREATMENT GROUP, DRUG CLASS AND PREFERRED NAME – COMBINED STAGE 1 AND STAGE 2	MITT POPULATION
TABLE 14.2.1.1.1	PRE-CAE® INFERIOR CORNEAL FLUORESCEIN STAINING (ORA CALIBRA® SCALE) – STAGE 1	MITT POPULATION WITH LOCF
TABLE 14.2.1.1.2	PRE-CAE® INFERIOR CORNEAL FLUORESCEIN STAINING (ORA CALIBRA® SCALE) – STAGE 2	MITT POPULATION WITH LOCF
TABLE 14.2.1.1.3	PRE-CAE® INFERIOR CORNEAL FLUORESCEIN STAINING (ORA CALIBRA® SCALE) – COMBINED STAGE 1 AND STAGE 2	MITT POPULATION WITH LOCF
TABLE 14.2.1.2.1	PRE-CAE® INFERIOR CORNEAL FLUORESCEIN STAINING (ORA CALIBRA® SCALE) – STAGE 1	MITT2 POPULATION WITH LOCF
TABLE 14.2.1.2.2	PRE-CAE® INFERIOR CORNEAL FLUORESCEIN STAINING (ORA CALIBRA® SCALE) – STAGE 2	MITT2 POPULATION WITH LOCF
TABLE 14.2.1.2.3	PRE-CAE® INFERIOR CORNEAL FLUORESCEIN STAINING (ORA CALIBRA® SCALE) – COMBINED STAGE 1 AND STAGE 2	MITT2 POPULATION WITH LOCF
TABLE 14.2.1.3.1	PRE-CAE® INFERIOR CORNEAL FLUORESCEIN STAINING (ORA CALIBRA® SCALE) – STAGE 1	PP POPULATION WITH LOCF
TABLE 14.2.1.3.2	PRE-CAE® INFERIOR CORNEAL FLUORESCEIN STAINING (ORA CALIBRA® SCALE) – STAGE 2	PP POPULATION WITH LOCF
TABLE 14.2.1.3.3	PRE-CAE® INFERIOR CORNEAL FLUORESCEIN STAINING (ORA CALIBRA® SCALE) – COMBINED STAGE 1 AND STAGE 2	PP POPULATION WITH LOCF
TABLE 14.2.1.4.1	PRE-CAE® INFERIOR CORNEAL FLUORESCEIN STAINING (ORA CALIBRA® SCALE) – STAGE 1	MITT POPULATION WITH OBSERVED DATA ONLY
TABLE 14.2.1.4.2	PRE-CAE® INFERIOR CORNEAL FLUORESCEIN STAINING (ORA CALIBRA® SCALE) – STAGE 2	MITT POPULATION WITH OBSERVED DATA ONLY
TABLE 14.2.1.4.3	PRE-CAE® INFERIOR CORNEAL FLUORESCEIN STAINING (ORA CALIBRA® SCALE) – COMBINED STAGE 1 AND STAGE 2	MITT POPULATION WITH OBSERVED DATA ONLY
TABLE 14.2.1.5.1	PRE-CAE® INFERIOR CORNEAL FLUORESCEIN STAINING (ORA CALIBRA® SCALE) – STAGE 1	MITT POPULATION WITH MCMC
TABLE 14.2.1.5.2	PRE-CAE® INFERIOR CORNEAL FLUORESCEIN STAINING (ORA CALIBRA® SCALE) – STAGE 2	MITT POPULATION WITH MCMC
TABLE 14.2.1.5.3	PRE-CAE® INFERIOR CORNEAL FLUORESCEIN STAINING (ORA CALIBRA® SCALE) – COMBINED STAGE 1 AND STAGE 2	MITT POPULATION WITH MCMC
TABLE 14.2.2.1.1	PRE-CAE® TOTAL CORNEAL FLUORESCEIN STAINING (ORA CALIBRA® SCALE) – STAGE 1	MITT POPULATION WITH LOCF
TABLE 14.2.2.1.2	PRE-CAE® TOTAL CORNEAL FLUORESCEIN STAINING (ORA CALIBRA® SCALE) – STAGE 2	MITT POPULATION WITH LOCF

Table Number	Title	Population
TABLE 14.2.2.1.3	PRE-CAE® TOTAL CORNEAL FLUORESCEIN STAINING (ORA CALIBRA® SCALE) – COMBINED STAGE 1 AND STAGE 2	MITT POPULATION WITH LOCF
TABLE 14.2.2.2.1	PRE-CAE® TOTAL CORNEAL FLUORESCEIN STAINING (ORA CALIBRA® SCALE) – STAGE 1	MITT2 POPULATION WITH LOCF
TABLE 14.2.2.2.2	PRE-CAE® TOTAL CORNEAL FLUORESCEIN STAINING (ORA CALIBRA® SCALE) – STAGE 2	MITT2 POPULATION WITH LOCF
TABLE 14.2.2.2.3	PRE-CAE® TOTAL CORNEAL FLUORESCEIN STAINING (ORA CALIBRA® SCALE) – COMBINED STAGE 1 AND STAGE 2	MITT2 POPULATION WITH LOCF
TABLE 14.2.2.3.1	PRE-CAE® TOTAL CORNEAL FLUORESCEIN STAINING (ORA CALIBRA® SCALE) – STAGE 1	PP POPULATION WITH LOCF
TABLE 14.2.2.3.2	PRE-CAE® TOTAL CORNEAL FLUORESCEIN STAINING (ORA CALIBRA® SCALE) – STAGE 2	PP POPULATION WITH LOCF
TABLE 14.2.2.3.3	PRE-CAE® TOTAL CORNEAL FLUORESCEIN STAINING (ORA CALIBRA® SCALE) – COMBINED STAGE 1 AND STAGE 2	PP POPULATION WITH LOCF
TABLE 14.2.2.4.1	PRE-CAE® TOTAL CORNEAL FLUORESCEIN STAINING (ORA CALIBRA® SCALE) – STAGE 1	MITT POPULATION WITH OBSERVED DATA ONLY
TABLE 14.2.2.4.2	PRE-CAE® TOTAL CORNEAL FLUORESCEIN STAINING (ORA CALIBRA® SCALE) – STAGE 2	MITT POPULATION WITH OBSERVED DATA ONLY
TABLE 14.2.2.4.3	PRE-CAE® TOTAL CORNEAL FLUORESCEIN STAINING (ORA CALIBRA® SCALE) – COMBINED STAGE 1 AND STAGE 2	MITT POPULATION WITH OBSERVED DATA ONLY
TABLE 14.2.2.5.1	PRE-CAE® TOTAL CORNEAL FLUORESCEIN STAINING (ORA CALIBRA® SCALE) – STAGE 1	MITT POPULATION WITH MCMC
TABLE 14.2.2.5.2	PRE-CAE® TOTAL CORNEAL FLUORESCEIN STAINING (ORA CALIBRA® SCALE) – STAGE 2	MITT POPULATION WITH MCMC
TABLE 14.2.2.5.3	PRE-CAE® TOTAL CORNEAL FLUORESCEIN STAINING (ORA CALIBRA® SCALE) – COMBINED STAGE 1 AND STAGE 2	MITT POPULATION WITH MCMC
TABLE 14.2.3.1.1	PRE-CAE® TOTAL CORNEAL FLUORESCEIN STAINING (OXFORD SCALE) – STAGE 1	MITT POPULATION WITH LOCF
TABLE 14.2.3.1.2	PRE-CAE® TOTAL CORNEAL FLUORESCEIN STAINING (OXFORD SCALE) – STAGE 2	MITT POPULATION WITH LOCF
TABLE 14.2.3.1.3	PRE-CAE® TOTAL CORNEAL FLUORESCEIN STAINING (OXFORD SCALE) – COMBINED STAGE 1 AND STAGE 2	MITT POPULATION WITH LOCF
TABLE 14.2.3.2.1	PRE-CAE® TOTAL CORNEAL FLUORESCEIN STAINING (OXFORD SCALE) – STAGE 1	MITT2 POPULATION WITH LOCF
TABLE 14.2.3.2.2	PRE-CAE® TOTAL CORNEAL FLUORESCEIN STAINING (OXFORD SCALE) – STAGE 2	MITT2 POPULATION WITH LOCF
TABLE 14.2.3.2.3	PRE-CAE® TOTAL CORNEAL FLUORESCEIN STAINING (OXFORD SCALE) – COMBINED STAGE 1 AND STAGE 2	MITT2 POPULATION WITH LOCF
TABLE 14.2.3.3.1	PRE-CAE® TOTAL CORNEAL FLUORESCEIN STAINING (OXFORD SCALE) – STAGE 1	PP POPULATION WITH LOCF
TABLE 14.2.3.3.2	PRE-CAE® TOTAL CORNEAL FLUORESCEIN STAINING (OXFORD SCALE) – STAGE 2	PP POPULATION WITH LOCF
TABLE 14.2.3.3.3	PRE-CAE® TOTAL CORNEAL FLUORESCEIN STAINING (OXFORD SCALE) – COMBINED STAGE 1 AND STAGE 2	PP POPULATION WITH LOCF
TABLE 14.2.3.4.1	PRE-CAE® TOTAL CORNEAL FLUORESCEIN STAINING (OXFORD SCALE) – STAGE 1	MITT POPULATION WITH OBSERVED DATA ONLY
TABLE 14.2.3.4.2	PRE-CAE® TOTAL CORNEAL FLUORESCEIN STAINING (OXFORD SCALE) – STAGE 2	MITT POPULATION WITH OBSERVED DATA ONLY

Table Number	Title	Population
TABLE 14.2.3.4.3	PRE-CAE® TOTAL CORNEAL FLUORESCEIN STAINING (OXFORD SCALE) – COMBINED STAGE 1 AND STAGE 2	MITT POPULATION WITH OBSERVED DATA ONLY
TABLE 14.2.3.5.1	PRE-CAE® TOTAL CORNEAL FLUORESCEIN STAINING (OXFORD SCALE) – STAGE 1	MITT POPULATION WITH MCMC
TABLE 14.2.3.5.2	PRE-CAE® TOTAL CORNEAL FLUORESCEIN STAINING (OXFORD SCALE) – STAGE 2	MITT POPULATION WITH MCMC
TABLE 14.2.3.5.3	PRE-CAE® TOTAL CORNEAL FLUORESCEIN STAINING (OXFORD SCALE) - COMBINED STAGE 1 AND STAGE 2	MITT POPULATION WITH MCMC
TABLE 14.2.4.1.1	PRE-CAE® EYE DRYNESS (VISUAL ANALOG SCALE) – STAGE 1	MITT POPULATION WITH LOCF
TABLE 14.2.4.1.2	PRE-CAE® EYE DRYNESS (VISUAL ANALOG SCALE) – STAGE 2	MITT POPULATION WITH LOCF
TABLE 14.2.4.1.3	PRE-CAE® EYE DRYNESS (VISUAL ANALOG SCALE) – COMBINED STAGE 1 AND STAGE 2	MITT POPULATION WITH LOCF
TABLE 14.2.4.2.1	PRE-CAE® EYE DRYNESS (VISUAL ANALOG SCALE) – STAGE 1	MITT2 POPULATION WITH LOCF
TABLE 14.2.4.2.2	PRE-CAE® EYE DRYNESS (VISUAL ANALOG SCALE) – STAGE 2	MITT2 POPULATION WITH LOCF
TABLE 14.2.4.2.3	PRE-CAE® EYE DRYNESS (VISUAL ANALOG SCALE) – COMBINED STAGE 1 AND STAGE 2	MITT2 POPULATION WITH LOCF
TABLE 14.2.4.3.1	PRE-CAE® EYE DRYNESS (VISUAL ANALOG SCALE) – STAGE 1	PP POPULATION WITH LOCF
TABLE 14.2.4.3.2	PRE-CAE® EYE DRYNESS (VISUAL ANALOG SCALE) – STAGE 2	PP POPULATION WITH LOCF
TABLE 14.2.4.3.3	PRE-CAE® EYE DRYNESS (VISUAL ANALOG SCALE) – COMBINED STAGE 1 AND STAGE 2	PP POPULATION WITH LOCF
TABLE 14.2.4.4.1	PRE-CAE® EYE DRYNESS (VISUAL ANALOG SCALE) – STAGE 1	MITT POPULATION WITH OBSERVED DATA ONLY
TABLE 14.2.4.4.2	PRE-CAE® EYE DRYNESS (VISUAL ANALOG SCALE) – STAGE 2	MITT POPULATION WITH OBSERVED DATA ONLY
TABLE 14.2.4.4.3	PRE-CAE® EYE DRYNESS (VISUAL ANALOG SCALE) – COMBINED STAGE 1 AND STAGE 2	MITT POPULATION WITH OBSERVED DATA ONLY
TABLE 14.2.4.5.1	PRE-CAE® EYE DRYNESS (VISUAL ANALOG SCALE) – STAGE 1	MITT POPULATION WITH MCMC
TABLE 14.2.4.5.2	PRE-CAE® EYE DRYNESS (VISUAL ANALOG SCALE) – STAGE 2	MITT POPULATION WITH MCMC
TABLE 14.2.4.5.3	PRE-CAE® EYE DRYNESS (VISUAL ANALOG SCALE) – COMBINED STAGE 1 AND STAGE 2	MITT POPULATION WITH MCMC
TABLE 14.2.5.1.1	PRE-CAE® TOTAL OSDI© SCORE – STAGE 1	MITT POPULATION WITH LOCF
TABLE 14.2.5.1.2	PRE-CAE® TOTAL OSDI© SCORE – STAGE 2	MITT POPULATION WITH LOCF
TABLE 14.2.5.1.3	PRE-CAE® TOTAL OSDI© SCORE – COMBINED STAGE 1 AND STAGE 2	MITT POPULATION WITH LOCF
TABLE 14.2.5.2.1	PRE-CAE® TOTAL OSDI© SCORE – STAGE 1	MITT2 POPULATION WITH LOCF
TABLE 14.2.5.2.2	PRE-CAE® TOTAL OSDI© SCORE – STAGE 2	MITT2 POPULATION WITH LOCF
TABLE 14.2.5.2.3	PRE-CAE® TOTAL OSDI© SCORE – COMBINED STAGE 1 AND STAGE 2	MITT2 POPULATION WITH LOCF
TABLE 14.2.5.3.1	PRE-CAE® TOTAL OSDI© SCORE – STAGE 1	PP POPULATION WITH LOCF
TABLE 14.2.5.3.2	PRE-CAE® TOTAL OSDI© SCORE – STAGE 2	PP POPULATION WITH LOCF
TABLE 14.2.5.3.3	PRE-CAE® TOTAL OSDI© SCORE – COMBINED STAGE 1 AND STAGE 2	PP POPULATION WITH LOCF
TABLE 14.2.5.4.1	PRE-CAE® TOTAL OSDI© SCORE – STAGE 1	MITT POPULATION WITH OBSERVED DATA ONLY
TABLE 14.2.5.4.2	PRE-CAE® TOTAL OSDI© SCORE – STAGE 2	MITT POPULATION WITH OBSERVED DATA ONLY

Table Number	Title	Population
TABLE 14.2.5.4.3	PRE-CAE® TOTAL OSDI© SCORE – COMBINED STAGE 1 AND STAGE 2	MITT POPULATION WITH OBSERVED DATA ONLY
TABLE 14.2.5.5.1	PRE-CAE® TOTAL OSDI© SCORE – STAGE 1	MITT POPULATION WITH MCMC
TABLE 14.2.5.5.2	PRE-CAE® TOTAL OSDI© SCORE – STAGE 2	MITT POPULATION WITH MCMC
TABLE 14.2.5.5.3	PRE-CAE® TOTAL OSDI© SCORE – COMBINED STAGE 1 AND STAGE 2	MITT POPULATION WITH MCMC
TABLE 14.2.6.1.1	FLUORESCEIN CORNEAL AND CONJUNCTIVAL STAINING (ORA CALIBRA® SCALE) – STAGE 1	MITT POPULATION WITH OBSERVED DATA ONLY
TABLE 14.2.6.1.2	FLUORESCEIN CORNEAL AND CONJUNCTIVAL STAINING (ORA CALIBRA® SCALE) – STAGE 2	MITT POPULATION WITH OBSERVED DATA ONLY
TABLE 14.2.6.1.3	FLUORESCEIN CORNEAL AND CONJUNCTIVAL STAINING (ORA CALIBRA® SCALE) – COMBINED STAGE 1 AND STAGE 2	MITT POPULATION WITH OBSERVED DATA ONLY
TABLE 14.2.6.2.1	FLUORESCEIN CORNEAL AND CONJUNCTIVAL STAINING (ORA CALIBRA® SCALE) BY SUBGROUP – STAGE 1	MITT POPULATION WITH OBSERVED DATA ONLY
TABLE 14.2.6.2.2	FLUORESCEIN CORNEAL AND CONJUNCTIVAL STAINING (ORA CALIBRA® SCALE) BY SUBGROUP – STAGE 2	MITT POPULATION WITH OBSERVED DATA ONLY
TABLE 14.2.6.2.3	FLUORESCEIN CORNEAL AND CONJUNCTIVAL STAINING (ORA CALIBRA® SCALE) BY SUBGROUP – COMBINED STAGE 1 AND STAGE 2	MITT POPULATION WITH OBSERVED DATA ONLY
TABLE 14.2.6.3.1	FLUORESCEIN CORNEAL AND CONJUNCTIVAL STAINING (ORA CALIBRA® SCALE) BY BASELINE MEDIAN – STAGE 1	MITT POPULATION WITH OBSERVED DATA ONLY
TABLE 14.2.6.3.2	FLUORESCEIN CORNEAL AND CONJUNCTIVAL STAINING (ORA CALIBRA® SCALE) BY BASELINE MEDIAN – STAGE 2	MITT POPULATION WITH OBSERVED DATA ONLY
TABLE 14.2.6.3.3	FLUORESCEIN CORNEAL AND CONJUNCTIVAL STAINING (ORA CALIBRA® SCALE) BY BASELINE MEDIAN – COMBINED STAGE 1 AND STAGE 2	MITT POPULATION WITH OBSERVED DATA ONLY
TABLE 14.2.7.1.1	FLUORESCEIN CORNEAL STAINING (OXFORD SCALE) – STAGE 1	MITT POPULATION WITH OBSERVED DATA ONLY
TABLE 14.2.7.1.2	FLUORESCEIN CORNEAL STAINING (OXFORD SCALE) – STAGE 2	MITT POPULATION WITH OBSERVED DATA ONLY
TABLE 14.2.7.1.3	FLUORESCEIN CORNEAL STAINING (OXFORD SCALE) – COMBINED STAGE 1 AND STAGE 2	MITT POPULATION WITH OBSERVED DATA ONLY
TABLE 14.2.7.2.1	FLUORESCEIN CORNEAL STAINING (OXFORD SCALE) BY SUBGROUP – STAGE 1	MITT POPULATION WITH OBSERVED DATA ONLY
TABLE 14.2.7.2.2	FLUORESCEIN CORNEAL STAINING (OXFORD SCALE) BY SUBGROUP – STAGE 2	MITT POPULATION WITH OBSERVED DATA ONLY
TABLE 14.2.7.2.3	FLUORESCEIN CORNEAL STAINING (OXFORD SCALE) BY SUBGROUP – COMBINED STAGE 1 AND STAGE 2	MITT POPULATION WITH OBSERVED DATA ONLY
TABLE 14.2.7.3.1	FLUORESCEIN CORNEAL STAINING (OXFORD SCALE) BY BASELINE MEDIAN – STAGE 1	MITT POPULATION WITH OBSERVED DATA ONLY
TABLE 14.2.7.3.2	FLUORESCEIN CORNEAL STAINING (OXFORD SCALE) BY BASELINE MEDIAN – STAGE 2	MITT POPULATION WITH OBSERVED DATA ONLY
TABLE 14.2.7.3.3	FLUORESCEIN CORNEAL STAINING (OXFORD SCALE) BY BASELINE MEDIAN – COMBINED STAGE 1 AND STAGE 2	MITT POPULATION WITH OBSERVED DATA ONLY
TABLE 14.2.8.1.1	VISUAL ANALOG SCALE – STAGE 1	MITT POPULATION WITH OBSERVED DATA ONLY
TABLE 14.2.8.1.2	VISUAL ANALOG SCALE – STAGE 2	MITT POPULATION WITH OBSERVED DATA ONLY

Table Number	Title	Population
TABLE 14.2.8.1.3	VISUAL ANALOG SCALE – COMBINED STAGE 1 AND STAGE 2	MITT POPULATION WITH OBSERVED DATA ONLY
TABLE 14.2.8.2.1	VISUAL ANALOG SCALE BY SUBGROUP – STAGE 1	MITT POPULATION WITH OBSERVED DATA ONLY
TABLE 14.2.8.2.2	VISUAL ANALOG SCALE BY SUBGROUP – STAGE 2	MITT POPULATION WITH OBSERVED DATA ONLY
TABLE 14.2.8.2.3	VISUAL ANALOG SCALE BY SUBGROUP – COMBINED STAGE 1 AND STAGE 2	MITT POPULATION WITH OBSERVED DATA ONLY
TABLE 14.2.8.3.1	VISUAL ANALOG SCALE BY BASELINE MEDIAN – STAGE 1	MITT POPULATION WITH OBSERVED DATA ONLY
TABLE 14.2.8.3.2	VISUAL ANALOG SCALE BY BASELINE MEDIAN – STAGE 2	MITT POPULATION WITH OBSERVED DATA ONLY
TABLE 14.2.8.3.3	VISUAL ANALOG SCALE BY BASELINE MEDIAN – COMBINED STAGE 1 AND STAGE 2	MITT POPULATION WITH OBSERVED DATA ONLY
TABLE 14.2.8.4.1	VISUAL ANALOG SCALE BY TIME TO CAE QUALIFICATION – STAGE 1	MITT POPULATION WITH OBSERVED DATA ONLY
TABLE 14.2.8.4.2	VISUAL ANALOG SCALE BY TIME TO CAE QUALIFICATION – STAGE 2	MITT POPULATION WITH OBSERVED DATA ONLY
TABLE 14.2.8.4.3	VISUAL ANALOG SCALE BY TIME TO CAE QUALIFICATION – COMBINED STAGE 1 AND STAGE 2	MITT POPULATION WITH OBSERVED DATA ONLY
TABLE 14.2.9.1.1	OCULAR SURFACE DISEASE INDEX (OSDI) – STAGE 1	MITT POPULATION WITH OBSERVED DATA ONLY
TABLE 14.2.9.1.2	OCULAR SURFACE DISEASE INDEX (OSDI) – STAGE 2	MITT POPULATION WITH OBSERVED DATA ONLY
TABLE 14.2.9.1.3	OCULAR SURFACE DISEASE INDEX (OSDI) – COMBINED STAGE 1 AND STAGE 2	MITT POPULATION WITH OBSERVED DATA ONLY
TABLE 14.2.9.2.1	OCULAR SURFACE DISEASE INDEX (OSDI) BY SUBGROUP – STAGE 1	MITT POPULATION WITH OBSERVED DATA ONLY
TABLE 14.2.9.2.2	OCULAR SURFACE DISEASE INDEX (OSDI) BY SUBGROUP – STAGE 2	MITT POPULATION WITH OBSERVED DATA ONLY
TABLE 14.2.9.2.3	OCULAR SURFACE DISEASE INDEX (OSDI) BY SUBGROUP – COMBINED STAGE 1 AND STAGE 2	MITT POPULATION WITH OBSERVED DATA ONLY
TABLE 14.2.9.3.1	OCULAR SURFACE DISEASE INDEX (OSDI) BY BASELINE MEDIAN – STAGE 1	MITT POPULATION WITH OBSERVED DATA ONLY
TABLE 14.2.9.3.2	OCULAR SURFACE DISEASE INDEX (OSDI) BY BASELINE MEDIAN – STAGE 2	MITT POPULATION WITH OBSERVED DATA ONLY
TABLE 14.2.9.3.3	OCULAR SURFACE DISEASE INDEX (OSDI) BY BASELINE MEDIAN – COMBINED STAGE 1 AND STAGE 2	MITT POPULATION WITH OBSERVED DATA ONLY
TABLE 14.2.9.4.1	OCULAR SURFACE DISEASE INDEX (OSDI) BY TIME TO CAE QUALIFICATION – STAGE 1	MITT POPULATION WITH OBSERVED DATA ONLY
TABLE 14.2.9.4.2	OCULAR SURFACE DISEASE INDEX (OSDI) BY TIME TO CAE QUALIFICATION – STAGE 2	MITT POPULATION WITH OBSERVED DATA ONLY
TABLE 14.2.9.4.3	OCULAR SURFACE DISEASE INDEX (OSDI) BY TIME TO CAE QUALIFICATION – COMBINED STAGE 1 AND STAGE 2	MITT POPULATION WITH OBSERVED DATA ONLY
TABLE 14.2.10.1.1	UNANESTHETIZED SCHIRMER'S TEST (MM) – STAGE 1	MITT POPULATION WITH OBSERVED DATA ONLY
TABLE 14.2.10.1.2	UNANESTHETIZED SCHIRMER'S TEST (MM) – STAGE 2	MITT POPULATION WITH OBSERVED DATA ONLY

Table Number	Title	Population
TABLE 14.2.10.1.3	UNANESTHETIZED SCHIRMER'S TEST (MM) – COMBINED STAGE 1 AND STAGE 2	MITT POPULATION WITH OBSERVED DATA ONLY
TABLE 14.2.10.2.1	UNANESTHETIZED SCHIRMER'S TEST (MM) STRATIFIED BY BASELINE MEDIAN – STAGE 1	MITT POPULATION WITH OBSERVED DATA ONLY
TABLE 14.2.10.2.2	UNANESTHETIZED SCHIRMER'S TEST (MM) STRATIFIED BY BASELINE MEDIAN – STAGE 2	MITT POPULATION WITH OBSERVED DATA ONLY
TABLE 14.2.10.2.3	UNANESTHETIZED SCHIRMER'S TEST (MM) STRATIFIED BY BASELINE MEDIAN – COMBINED STAGE 1 AND STAGE 2	MITT POPULATION WITH OBSERVED DATA ONLY
TABLE 14.2.11.1.1	TEAR FILM BREAK-UP TIME (TFBUT) – STAGE 1	MITT POPULATION WITH OBSERVED DATA ONLY
TABLE 14.2.11.1.2	TEAR FILM BREAK-UP TIME (TFBUT) – STAGE 2	MITT POPULATION WITH OBSERVED DATA ONLY
TABLE 14.2.11.1.3	TEAR FILM BREAK-UP TIME (TFBUT) – COMBINED STAGE 1 AND STAGE 2	MITT POPULATION WITH OBSERVED DATA ONLY
TABLE 14.2.11.2.1	TEAR FILM BREAK-UP TIME (TFBUT) STRATIFIED BY BASELINE MEDIAN – STAGE 1	MITT POPULATION WITH OBSERVED DATA ONLY
TABLE 14.2.11.2.2	TEAR FILM BREAK-UP TIME (TFBUT) STRATIFIED BY BASELINE MEDIAN – STAGE 2	MITT POPULATION WITH OBSERVED DATA ONLY
TABLE 14.2.11.2.3	TEAR FILM BREAK-UP TIME (TFBUT) STRATIFIED BY BASELINE MEDIAN – COMBINED STAGE 1 AND STAGE 2	MITT POPULATION WITH OBSERVED DATA ONLY
TABLE 14.2.12.1.1	OCULUS KERATOGRAPH – STAGE 1	MITT POPULATION WITH OBSERVED DATA ONLY
TABLE 14.2.12.1.2	OCULUS KERATOGRAPH – STAGE 2	MITT POPULATION WITH OBSERVED DATA ONLY
